**Additional treatments focusing on inflammatory and oxidative pathways are needed to improve the health of obese asthmatics with metabolic syndrome.** Several of the pharmacological properties of nitrite, nitrate and CLA make them ideal candidates to overcome many of the metabolic and inflammatory factors associated with obesity, especially when coexisting with MS. For example, nitrate has been shown to improve endothelial function, reduce blood pressure and insulin resistance in diabetic patients (32). Another relevant aspect of NOx therapy is that it may increase airway NO bioavailability by providing an alternative source of NO other than NOS, which could be particularly useful in situations, such as obesity, when the L-arginine/ADMA balance favors iNOS uncoupling. CLA is a polyunsaturated fatty acid found in dairy products and ruminant meat (i.e. beef) and an average American diet supplies 15-174 mg of CLA daily. Moreover, CLA is formed in the body following conversion of linoleic acid to CLA by bacteria of the gastrointestinal tract. CLA has pleiotropic anti-inflammatory actions, including partial PPARγ agonist activity, NF-κB inhibition and Nrf2 activation. Clinically, CLA has been associated with a wide range of salutary effects including: decreased body fat mass in obese and healthy overweight patients (33, 34), decreased the leptin/adiponectin ratios, and reduced risk of colorectal cancer. Of particular relevance to obesity and asthma, CLA has been shown to suppress Th-1 and Th17-mediated inflammatory responses in dendritic cells (14). This effect could be relevant to obese late-onset asthmatics who have a greater Th1 polarization and in whom Th17 responses appear to play a major role. Also, its ability to decrease the leptin/adiponectin ratio could ameliorate airway inflammation. Clinically, CLA has been shown to be potentially effective in improving bronchial hyperresponsiveness in obese and overweight mild asthmatics randomized to receive CLA 4,560 mg/d for 12 weeks. Compared to placebo,

those receiving CLA, had a significant reduction in the average methacholine dose to achieve a 20% reduction in FEV1 (change in methacholine dose from pre to post treatment was 5mg/ml [1.9] in the CLA arm vs 1.2 [1.2] in the placebo, p=0.02). Interestingly, this occurred in the absence of any significant changes in systemic biomarkers of airway inflammation; however, the study did not include any airway measurements (10).

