## 5 RESEARCH DESIGN AND METHODS

### 5.1 Study Design

This is an open-label, single center, proof of concept pilot study in obese asthmatics.

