## **8 STATISTICAL ANALYSIS AND POWER CALCULATIONS**

### **8.1 Sample Size Determination**

To ensure 90% power to detect a difference in the change in the methacholine dose required to produce a PC20 before and after treatment, a sample size of n=12 participants will be required. This estimate assumes an alpha level of 0.05, and a 2-sided test. The estimate of variability and effect size used was by McRedmond et al, in which the PC20 effect size associated with CLA administration was 3.8 (SD 1.9). There are no preliminary data on how CLA or NOx + CLA affect exhaled NO and therefore are unable to reasonably anticipate a sample size for adequate power.

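### Section 8.1 labels 1.9 as an SD, but this does not agree with the p=0.02 quoted in section 2 for the same data unless the source arms held about 4 patients, so the 90% power is unsupported

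*Combined protocol and SAP*

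**What the plan says.** Section 8.1 sets the aim as follows: "To ensure 90% power to detect a difference in the change in the methacholine dose required to produce a PC20 before and after treatment", and concludes that "a sample size of n=12 participants will be required". On the error rate it says "This estimate assumes an alpha level of 0.05, and a 2-sided test". Its inputs come from an earlier randomised trial of CLA, in which "the PC20 effect size associated with CLA administration was 3.8 (SD 1.9". It adds that exhaled NO could not be powered for want of preliminary data, so this is the only power statement in the plan.

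The last part of section 2 (Background and Rationale) describes the same trial, in "obese and overweight mild asthmatics randomized to receive CLA 4,560 mg/d for 12 weeks". It gives the result as: "change in methacholine dose from pre to post treatment was 5mg/ml [1.9] in the CLA arm vs 1.2 [1.2] in the placebo, p=0.02". Nothing there says whether the square brackets are standard deviations, standard errors or something else.

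Section 5.1 describes the present design: "This is an open-label, single center, proof of concept pilot study in obese asthmatics". Section 8.3 plans matched before-and-after comparisons. There is no concurrent control group.

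**The concern.** The two sections use the same numbers. The 3.8 in section 8.1 is 5 − 1.2 from section 2, and the 1.9 is the CLA-arm bracket. Only section 8.1 attaches the label SD. If that label is right, a difference of 3.8 is two standard deviations, and a trial of any ordinary size would have produced a p-value far below 0.02. The label and the p-value are therefore in tension.

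The power claim depends directly on this input. If the SD of a participant's change is well above 1.9, 12 pairs may fall short of 90% power. Section 9.1.1 says the methacholine challenge is done mainly to check that treatment does not increase airway responsiveness. A null PC20 result read against a nominal 90% power could then reassure more than it should. Correcting only the formula would not help, because keeping SD 1.9 in a paired calculation gives power above 99.9%.

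**Working it through.** **Inputs.** From section 8.1: effect 3.8, SD 1.9, two-sided alpha 0.05, power 90%, n=12. From section 2: CLA 5 [1.9], placebo 1.2 [1.2], p=0.02. The source trial's arm size m is not in the documents. I assume 8 to 15 per arm and also check smaller arms.

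**1. The plan's own figure.** The standardised effect is 3.8/1.9 = 2.0. The two-arm normal formula gives 2 × (1.960 + 1.282)² / 2.0² = 5.25, so 6 per arm and 12 in total. That reproduces 12, but for two arms. The paired t-test planned in 8.3, with an SD of change of 1.9, needs 5 participants (90.9% power) and exceeds 99.9% power at 12. This mismatch is separate from the question of the input.

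**2. Does SD 1.9 fit p=0.02?** Take both brackets as SDs. The pooled SD with equal arms is √((1.9² + 1.2²)/2) = 1.589, and t = 3.8 / (1.589 × √(2/m)) on 2m − 2 degrees of freedom.

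| m per arm | t | two-sided p |
|---|---|---|
| 3 | 2.93 | 0.043 |
| 4 | 3.38 | 0.015 |
| 5 | 3.78 | 0.005 |
| 8 | 4.78 | 0.0003 |
| 10 | 5.35 | 0.00004 |

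The unequal-variance version gives 0.019 at 4 per arm and 0.0005 at 8. Only about 4 per arm agrees with 0.02.

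**3. Does a standard error fit better?** Between arms, t = 3.8 / √(1.9² + 1.2²) = 3.8/2.247 = 1.69, and p is 0.11 at 8 per arm and 0.10 at 15. That is not 0.02 either. Within the CLA arm alone, t = 5/1.9 = 2.63, which gives p = 0.023 with 12 patients and 0.020 with 15. A standard error is possible but not shown.

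**4. Power of 12 pairs under each reading.** The figures are for a paired t-test by the noncentral t, two-sided 0.05. The back-solved SD assumes a common SD in both arms: SD = 3.8 / (t₀.₉₉,₂ₘ₋₂ × √(2/m)). At m=8 this is 3.8 / (2.624 × 0.5) = 2.90. The standard-error reading gives SD = 1.9√m, which at m=8 is 5.37.

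| Reading of the source | m | SD | Power for 3.8 | Power for 5 |
|---|---|---|---|---|
| SD back-solved from p=0.02 | 8 | 2.90 | 98% | over 99% |
| | 10 | 3.33 | 95% | over 99% |
| | 15 | 4.22 | 81% | 96% |
| 1.9 is a standard error | 8 | 5.37 | 61% | 83% |
| | 10 | 6.01 | 52% | 75% |
| | 15 | 7.36 | 37% | 57% |

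The column for 5 is there because a single-group paired test sees the uncontrolled change, and 5 is that change in the source's CLA arm. The 3.8 has the placebo change removed. If the back-solved SDs keep the 1.9 to 1.2 ratio instead of being equal, the CLA-arm SD is 3.46 to 5.04, and power is 93% to 66% for 3.8 and over 99% to 88% for 5.

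**5. What 12 pairs detect.** A mean change of 1.03 SD has 90% power and one of 0.89 SD has 80%. So 90% power for 3.8 needs an SD of change of at most 3.8/1.029 = 3.7.

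**The case against.** The strongest reply is that a p-value cannot be checked without knowing how it was obtained. The documents give no arm size, test, scale or adjustment for the source trial. A rank test, a log-scale analysis or an adjusted model need not match a t-test rebuilt from two means and two brackets. Section 2 is also a loose paraphrase: it describes the benefit as a fall in the methacholine dose needed, although lower reactivity would be a rise. The p-value or a bracket could simply have been misquoted. All of this stands. It rules out saying that SD 1.9 is impossible, and it rules out inferring that 1.9 must be a standard error, since that reading gives a between-arm p of about 0.10.

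It is also fair that the shortfall may not exist. With a common back-solved SD, power for 3.8 lies on both sides of 90%, and for a change of 5 it stays above 90% throughout the assumed range. A reader might infer that the trial is underpowered for PC20. The documents do not support so firm a statement.

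A reader might also scale the expected effect down, because the source patients were "randomized to receive CLA 4,560 mg/d for 12 weeks" and the present plan gives 3,000 mg/day for 8 weeks. No passage supports proportionality to dose or duration, and the present intervention adds NOx. I draw no power figure from that.

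Finally, PC20 is not the primary outcome, the study is a pilot, and no decision rule is tied to PC20. This lowers the severity. None of it reconciles SD 1.9 with p=0.02 for larger arms under the comparison as section 2 presents it.

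**Conclusion.** The concern holds in a limited form. Under a two-sample t-test on the reported scale, the SD label in section 8.1 and the p-value in section 2 agree only at about 4 patients per source arm. The stated 90% power is therefore unsupported, which is different from shown to be wrong. Assuming 8 to 15 patients per source arm and a common SD where it is back-solved, power with 12 pairs lies between 37% and 98% for 3.8, and between 57% and over 99% for an uncontrolled change of 5. Where it falls depends on what the 1.9 is and which effect is the target. Severity is moderate and confidence is moderate. The arithmetic is secure, but the source's arm size, test and scale are unknown.

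**What to change.** Rewrite the paragraph in section 8.1 and reconcile it with section 2:

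- Check in the source report whether 1.9 is a standard deviation or a standard error, and of which quantity. Label the brackets in section 2 and confirm which comparison the p=0.02 belongs to.
- Replace SD 1.9 with the SD of the within-participant change.
- Say whether the target is the placebo-subtracted 3.8 or the uncontrolled before-and-after change.
- State what 12 pairs can detect with a two-sided paired test at 0.05: 1.03 SD of the change at 90% power and 0.89 SD at 80%. Give power over the plausible range of SDs.
- Drop the flat 90% figure unless it survives this.

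The cost is one look at the source report and one rewritten paragraph, with a label added in section 2. The sample size, visits and analyses do not change. The stated power may become less favourable.

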## **8.2 Study Conduct Analyses**

Deviations will not be distinguished from protocol violations; any failure to follow the protocol will be defined and recorded as a protocol violation. Such violations should be reported to the local Investigational Review Board (IRB) as per required practice. No exceptions to the eligibility criteria for the study are permitted.

## **8.3 Efficacy Analyses**

Primary analysis: The primary analysis will test whether there is a significant difference in exhaled NO and measures of airway oxidative stress (superoxide production, XO activity in biopsies) before and after taking either of the intervention arms. This analysis will utilize an approach of comparing average values pre and post intervention, using matched paired comparisons.

Matched analysis are very efficient in controlling for confounders, as the analysis uses the same individual as case and control under different treatment conditions. Secondary outcomes will be tested following the same scheme of pre and post matched comparisons. To determine the relevance of measured variables, these will be compared to results from healthy controls undergoing bronchoscopy as part of the Electrophilic Fatty Acid Derivatives in Asthma (EFADA) study (IRB#: PRO11010186). This analysis will allow cross sectional comparisons and determine, for example, how obesity influences some of the baseline study variables.

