### **3 STUDY HYPOTHESES**

#### **3.1 Primary Hypothesis**

We hypothesize that in obese asthmatics; treatment with NOx + CLA is well tolerated, safe and will increase eNO while reducing airway oxidative stress.

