### **4 STUDY OUTCOMES**

#### **4.1 Primary Outcome**

To determine how CLA + NOx affect airway NO bioavailability and oxidative stress

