#### **4.2 Secondary Outcomes**

To determine whether, compared to baseline, treatment with NOx + CLA can:

- a) Increases eNO levels
- b) Quantify the concentrations of nitrate/nitrite in plasma and urine, free cLA in plasma, and NO2-cLA in BALF, plasma, and urine
- c) Reduce airway oxidation and inflammation
  - a. Western and RTPCR NF-κB and Nrf2 pathways in airway macrophages and PBMCs
  - b. Airway leptin and adiponectin
  - c. Proportion of airway TH-17 cells/responses

- d) Airway XO activity determined in endobronchial biopsies
- e) Measurement of  $^{15}\text{NO}_2\text{-cLA}$  and endogenous  $^{14}\text{NO}_2\text{-cLA}$  in urine, plasma and BAL
- f) Decrease production of anion superoxide in fresh airway epithelial cells;
- g) Mitochondrial ROS production and bioenergetics in fresh and cultured airway epithelial cells. As a potential source for airway / epithelial oxidative stress

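### Exhaled NO, superoxide and XO activity are primary in Section 8.3 but secondary in Section 4.2, with no success rule or named exhaled NO visits, and the 90% power in Section 8.1 does not describe the planned paired test

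*Combined protocol and SAP*

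**What the plan says.** - **Section 8.3** describes a primary analysis that "will test whether there is a significant difference in exhaled NO and measures of airway oxidative stress (superoxide production, XO activity in biopsies", by "comparing average values pre and post intervention, using matched paired comparisons". It adds that secondary outcomes follow the same scheme, so it treats the two sets as distinct.
- **Section 4.2** lists as secondary (a) "Increases eNO levels", (d) "Airway XO activity determined in endobronchial biopsies" and (f) "Decrease production of anion superoxide in fresh airway epithelial cells".
- **Section 4.1** gives the primary outcome as how the treatment may "affect airway NO bioavailability and oxidative stress". It names no measure and no visit.
- **Section 3.1** hypothesises that treatment is tolerated and safe and "will increase eNO while reducing airway oxidative stress". **Section 3.2** makes reduced oxidative stress in airway epithelial cells an exploratory hypothesis.
- **Section 6** schedules exhaled NO (eNO) at Visits 1, 2 and 3 before treatment, at Visit 4 during it, and at Visits 5 and 6 at the end.
- **Section 8.1** sets n=12 for 90% power on change in PC20 (effect 3.8, SD 1.9, two-sided 0.05) and says openly that no sample size could be set for eNO.
- **Section 8.5** says that likelihood-based methods will be used for primary and secondary outcomes.
- **Section 8.3** also speaks of values "before and after taking either of the intervention arms", although Sections 5.1 and 5.2 describe one open-label treatment.

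**The concern.** Three variables carry two ranks each, and superoxide in epithelial cells arguably carries a third. Nothing says whether one significant result, all three, or some combination supports the primary claim. A report could call a favourable variable primary by citing Section 8.3, or an unfavourable one secondary by citing Section 4.2, and in either case follow the plan. For eNO, the terms pre and post leave the visit pair open, which is a second free choice. The study is open label and has no control group, so fixing these choices in advance is one of the few protections it has. The only power figure concerns a measure that is in no Section 4 list, and it does not describe the single-group test that is planned.

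**Working it through.** **1. Ranks side by side**

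| Variable | 3.2 | 4.1 | 4.2 | 8.3 |
|---|---|---|---|---|
| eNO | – | not named | secondary (a) | primary |
| XO activity | – | not named | secondary (d) | primary |
| Superoxide, epithelial cells | exploratory, by overlap | not named | secondary (f) | primary |

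**2. Error and power under the possible rules.** Two-sided 0.05 per test is an assumption, because the plan states it only in Section 8.1, for PC20. Correlations are also assumed; the documents give none.

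- *Any one of three suffices.* Independent tests: 1 − 0.95³ = 0.143. Simulated paired t-tests (n=12, 200,000 runs) give 0.143, 0.128 and 0.103 at correlation 0, 0.5 and 0.8. Counting only the hypothesised direction: 1 − 0.975³ = 0.073 when independent, simulated 0.074, 0.063 and 0.051, against 0.025 for one test.
- *All three required.* Error does not inflate, but joint power falls. Independent tests give 0.9³ = 0.729 or 0.8³ = 0.512. Over correlations 0 to 0.8 the simulated range is 73–82% if each has 90%, and 51–68% if each has 80%.
- *eNO plus at least one oxidative-stress measure.* The choice between the two oxidative measures inflates: 1 − 0.95² = 0.0975 if they are independent and neither changes.

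**3. eNO visit pair.** Superoxide and XO activity need bronchoscopy samples, so Visits 3 and 6 are fixed for them. For eNO, assume equal variances and error correlation r between end visits.

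- Visit 3 (labelled Week 0) as baseline, free choice of Visit 5 or 6: the two differences correlate at (1 + r)/2, that is 0.5, 0.75 and 0.9 for r = 0, 0.5 and 0.8. Simulated error is 0.092, 0.082 and 0.072.
- Best of all six pairs (three pre, two end), with the same r within each period: 0.226, 0.175 and 0.122.

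**4. The n=12 in Section 8.1**

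- Source of 3.8: Section 2 reports a PC20 change of 5 on CLA and 1.2 on placebo in the cited trial, and 5 − 1.2 = 3.8. This is a between-arm difference.
- Two-group normal approximation: 2 × [1.9 × (1.960 + 1.282)/3.8]² = 5.25, so 6 per group and 12 in total. This matches the plan's figure. A two-sample t-test does not: 6 per group gives 87.6%, and 7 per group (14) is needed.
- Planned paired t-test with 3.8/1.9 = 2: n=4 gives 75.5%, n=5 gives 90.9%, n=12 gives over 99.9%.
- If 1.9 is a per-visit SD with zero correlation, the SD of change is 1.9 × √2 = 2.69 and power at n=12 is 99.3%.
- For n=12 to give 90%, the SD of change would be 3.8/1.029 = 3.69.

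**5. What 12 completers can detect** (mean change divided by SD of change, noncentral t)

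| Level | 80% power | 90% power |
|---|---|---|
| 0.05 | 0.89 | 1.03 |
| 0.0167 (first Holm step, 0.05/3) | 1.08 | 1.23 |

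**The case against.** This is a proof-of-concept pilot, so family-wise error matters less than in a confirmatory trial, and Section 8.1 is candid that eNO was not sized. Both points are fair and limit the weight of the concern. They do not settle the rank of the three variables, and Section 8.3 still specifies a significance test and calls it primary.

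Some stronger readings are tempting, but the documents do not support them:

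- *eNO at Visits 3 and 6 is measured after bronchoscopy because it is listed after it.* The lists are not reliably in time order. Visit 3 lists blood work after bronchoscopy, while the bronchoscopy procedure description draws blood at IV placement, beforehand. Visit 1 also lists eNO after albuterol spirometry. The timing is unclear, and no more can be said.
- *The labelled nitrate/nitrite dose sets Visit 6 apart.* The Visit 5 instructions have it replace the regular supplement at the same dose. The timing conflict (24 hours before bronchoscopy in Section 5.2, about 12 hours under Visit 5) is real but separate.
- *Visit choice inflates error to 12–23%.* That needs screening visits to serve as baselines and the best of six pairs to be picked. Visit 3 is Week 0, and the abstract's pre- and post-intervention bronchoscopies point to Visits 3 and 6.
- *Sections 8.3 and 8.5 contradict each other.* They can be compatible: with two visits and complete data, a likelihood-based repeated-measures model gives the same contrast as the paired test. The text needs to say which applies.
- *Section 3.1 requires all three to be significant.* It requires higher eNO and less oxidative stress. One oxidative measure could satisfy that.
- *The trial is too small for PC20, or PC20 was overlooked.* On the stated inputs n=12 is more than enough. Section 8.4 monitors bronchial hyperresponsiveness, and Section 9.1.1 calls the methacholine test primarily a safety measure.

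**Conclusion.** The concern holds and should be fixed. The rank conflict between Sections 4.2 and 8.3, the missing success rule and the unnamed eNO visits are evident from the text.

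The error rate is 10–14% if any one of three suffices, and 7–9% from choosing the eNO end visit with Visit 3 as baseline. The 12–23% over six pairs is a worst case only. These figures assume two-sided 0.05 per test and correlations from 0 to 0.8.

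The 90% in Section 8.1 does not describe the planned test. On 3.8 and 1.9 it is conservative, provided that 1.9 is an SD as Section 8.1 says (Section 2 leaves its bracketed figures unlabelled) and that the SD of change stays well below 3.69. That a two-group formula produced n=12 is an inference from the match, not something the plan states. For the primary variables, 12 completers give 90% power only for changes of about one SD of change or more.

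**What to change.** All changes should be made before data are seen.

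1. Give each variable one rank across Sections 3.2, 4.1, 4.2 and 8.3. *Either* make eNO the single primary at two-sided 0.05, rewrite 4.1 to match, and keep XO activity and superoxide secondary. *Or* make all three primary, remove them from 4.2 and state the rule: Holm if any one suffices, or a joint requirement at 0.05 each. If the joint requirement is eNO plus at least one oxidative measure, apply Holm between those two.
2. In 8.3, name one eNO baseline visit and one end-of-treatment visit, with the other visits as sensitivity analyses. State when eNO is measured relative to bronchodilator and bronchoscopy. Separately, reconcile the labelled-dose timing in Section 5.2 and under Visit 5.
3. State one analysis in 8.3 and 8.5: the paired test, or a likelihood-based repeated-measures model with the named visit contrast. Delete the reference to intervention arms.
4. In 8.1, replace the 90% with the power of the single-group paired test and its SD-of-change assumption. State that n=12 is not sized for the primary variables, and give the detectable changes from the working.

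Listing PC20 in Section 4 as a safety outcome is optional tidying.

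The cost is protocol wording, with no added participants, visits or assays. A single primary takes primary status from XO activity and superoxide. Holm raises the first-step detectable change from 0.89 to 1.08 SD (80% power) or from 1.03 to 1.23 SD (90%). Requiring all three lowers joint power.

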**Specific Aim 2.** To determine whether treatment with **NOx + CLA** can influence airway NO bioavailability, as well as oxidative, metabolic and inflammatory pathways. Participants will undergo pre and post-treatment bronchoscopies to obtain airway epithelial cells, bronchoalveolar lavage fluid (BALF) and endobronchial biopsies. Peripheral blood and urine will also be collected at each of these bronchoscopies. To do this, we will compare the following pre and post intervention endpoints: a) total CLA levels, nitrite/nitrate in urine and plasma, and NO2-cLA levels in BALF, plasma, and urine; b) NFκB and Nrf2 pathways in peripheral blood monocyte cells (PBMC) and alveolar macrophages, c) leptin/adiponectin in BAL and plasma, d) plasma ADMA e) airway microbiome in BAL f) airway xanthine oxidase (XO) activity from endobronchial biopsies (as an airway oxidative stress source), g) TH17: BAL fluid/cells: IL-17 levels, mRNA, flow cytometry, h) metabolomics study to look at where N is incorporated other than NO2-cLA; to do this, participants will take same dose of nitrate and nitrite N heavy isotopes, the day prior to the second bronchoscopy.

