### 5.2 Description of the Study Design

Potential subjects will be recruited from the Asthma Institute registry and the CTSI registry, and throughout the community at large. After an initial screen visit, those who sign the consent and meet eligibility will proceed to have methacholine testing; subjects with a > 12% bronchodilation in FEV1, or achieving a 20 % reduction in FEV1 from baseline (PC20) after methacholine, will receive **NOx + CLA** for a period of 8 weeks.

\* 15Nox dose will be taken 24 hours prior to V6 bronchoscopy

\*\*An additional visit might be needed in some participants to perform pre- and post-spirometry after an adequate medication withhold

Prior to treatment, participants will undergo a baseline bronchoscopy at UPMC Montefiore, after which they will be instructed to begin taking the assigned intervention for 8 weeks. At the completion of the treatment period, participants will undergo a second methacholine challenge and a final bronchoscopy.

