#### Visit 5 (after 8 weeks of treatment)

- ACQ
- Urine pregnancy test in females of child-bearing potential
- Exhaled nitric oxide test
- Brief physical exam
- Methacholine testing- This is a common test often used to confirm a diagnosis of asthma. Methacholine is a chemical that causes the airways to react (narrow) and is easily reversed with the administration of albuterol. Prior to the test, a urine pregnancy test will be performed on women of childbearing potential and a blood pressure reading will be taken. An exhaled nitric oxide test and a brief physical exam will also be performed. The challenge test consists of inhaling very low, but increasing doses of methacholine through a nebulizer to assess how quickly the airways narrow. Spirometry (focusing on the FEV-1) will be performed approximately 30 and 90 seconds after each dose to look for changes in lung function. If/when a 20% decrease in spirometry (FEV-1) is observed the challenge test will be stopped. Multiple measures are in place to perform this test safely and comfortably. Subjects will receive albuterol after the test is done.
- Patient is instructed to take Nitrogen 15 sodium nitrate and 15 sodium nitrite in substitution of regular NOx supplements (same dose) with food approximately 12 h prior to bronchoscopy. This dose is in a form that is easily observed in study samples.
- Dispense study drug supply

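### The pre/post test in Section 8.3 cannot show a treatment effect on 15N-labelled products, because the label is given only before Visit 6

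*Combined protocol and SAP*

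**What the plan says.** Section 8.3 sets one rule for all secondary outcomes: "Secondary outcomes will be tested following the same scheme of pre and post matched comparisons". Section 4.2 introduces its list with "To determine whether, compared to baseline, treatment with" the combination. Item e on that list is the measurement of 15NO2-cLA and endogenous 14NO2-cLA in urine, plasma and BAL. Under Specific Aim 2 the protocol says "we will compare the following pre and post intervention endpoints", and item h of that list is metabolomics to trace where 15N goes other than into NO2-cLA.

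The label is given once, as a swap for the usual product. At Visit 5: "Patient is instructed to take Nitrogen 15 sodium nitrate and 15 sodium nitrite in substitution of regular NOx supplements (same dose"). Section 5.3 describes the daily capsules as standard nitrite and nitrate, and no labelled dose is scheduled before the Visit 3 bronchoscopy. Plasma, urine and BAL are collected at both Visit 3 and Visit 6.

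The time of the labelled dose is given in three ways:
- Aim 2 h: "the day prior to the second bronchoscopy"
- Section 5.2, footnote: "15Nox dose will be taken 24 hours prior to V6 bronchoscopy"
- Section 6, Visit 5: "with food approximately 12 h prior to bronchoscopy"

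No other analysis of the labelled species is described.

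**The concern.** Section 8.3 justifies the matched design on the ground that each person serves as their own control under different treatment conditions. For a labelled product, the two visits differ in a second respect: label was given before one and not before the other. A rise from Visit 3 to Visit 6 is what one would see if any of the single labelled dose reached the measured product, so the paired contrast cannot separate that from the effect of eight weeks of treatment.

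At stake is a p-value reported as a change from baseline with treatment, in a small uncontrolled proof-of-concept study, when it answers a different question. Formation of 15NO2-cLA after a labelled dose is of real interest, but it is a Visit 6 estimate and not a change.

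**Working it through.** **Plan's own figure.** The plan gives no design figure for the labelled outcome. Its only one is n = 12 in Section 8.1, for methacholine PC20 (effect 3.8, SD 1.9, two-sided alpha 0.05, power 90%). A two-sample normal formula reproduces it: 2 × (1.960 + 1.282)² × (1.9/3.8)² = 5.3, rounded up to 6 per arm, 12 in total. Whether that formula suits a single-arm study is a separate question. Here 12 is only the number of pairs.

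**Step 1: what each visit's value contains.**
- Visit 3: treatment not started, no label given. 15N species: background. 14N species: a true baseline.
- Visit 6: about eight weeks of standard product, then one labelled dose in place of the regular one. 15N species: whatever that dose produced. 14N species: everything not derived from that dose.

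The difference in the 15N species is therefore background subtracted from the yield of one dose. Eight weeks of treatment may influence that yield, but no labelled dose was given without treatment to compare it with.

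**Step 2: when the test would be significant.** Take the baselines as zero and suppose label is detected in k of 12 participants. All non-zero differences are then positive, and the exact two-sided signed-rank (or sign) test gives p = 2 × 0.5^k:

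| k detected | p |
|---|---|
| 5 | 2 × 0.5^5 = 0.0625 |
| 6 | 2 × 0.5^6 = 0.031 |
| 8 | 2 × 0.5^8 = 0.0078 |
| 12 | 2 × 0.5^12 = 0.0005 |

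The threshold is 6 of 12, and the amount of label does not enter.

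**Step 3: how likely that is.** The documents give no detection probability, so q per participant is assumed. The chance of a significant result is P(X ≥ 6), X binomial(12, q):

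| q | chance |
|---|---|
| 0.10 | 0.0005 |
| 0.25 | 0.05 |
| 0.50 | 0.61 |
| 0.75 | 0.99 |
| 0.95 | 1.00 |

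**Step 4: a paired t-test instead.** Section 8.3 speaks of comparing average values, so this reading is also open. If all 12 post values are detectable and lognormal with an assumed coefficient of variation of 0.5, 1 or 2, the t-test rejects in 100%, 98% or 81% of simulations. If k participants show equal amounts and the rest none, it reaches p = 0.039 at k = 4.

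Under either test, the result follows how often label is detected (for the t-test, also how variable the amounts are). It does not follow a treatment contrast.

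**The case against.** The strongest reply is that the labelled dose is plainly a tracer. Item 4.2 e speaks of measurement and names no direction, Aim 2 h states a tracing purpose, and the opening of 4.2 does not fit several of its items grammatically. On that view nobody intends a pre/post test of 15NO2-cLA. This may well be the intention, but Section 8.3 says secondary outcomes will be tested, makes no exception, and gives no alternative. If description is meant, a sentence should say so.

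A reader might also infer more than the documents support:
- *That the test is positive by construction.* It is not. It needs detectable incorporation in about half the participants, and whether that occurs is an open question of the study. The value 0.0005 assumes 12 of 12.
- *That there is no pre-treatment value.* Visit 3 plasma, urine and BAL exist and can be assayed. They give background, which is useful as a blank.
- *That one labelled dose in an untreated person would give the same result.* Nothing shows this. NO2-cLA forms by nitration of CLA, and at Visit 6 participants have taken 3,000 mg/day against the 15-174 mg/day cited for an average diet, so loading could alter the yield. The design simply cannot show whether it does.
- *That all of item e is affected.* Endogenous 14NO2-cLA has a genuine baseline.
- *That Section 8.3 itself covers Aim 2 h.* That item is not on the 4.2 list. Its pre/post framing comes from the Aim 2 lead-in.

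It is also fair that the primary analysis, sample size and safety monitoring are untouched.

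**Conclusion.** The concern holds for the 15N-labelled species only. As written, the plan puts 15NO2-cLA through a matched test whose baseline is background by design, and the Aim 2 lead-in does the same for the 15N metabolomics. The test is uninformative about an effect of eight weeks of treatment, and it is likely to be significant if label is detectable in about half or more of the 12 participants (p = 0.031 at 6, 0.0005 at 12).

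These p-values assume 12 complete pairs, baselines of exactly zero and a signed-rank test. Noisy background or missing pairs would change them. The main conclusion does not depend on them: it rests on the timing of the label, and all three descriptions place it before the second bronchoscopy only. This is a secondary-outcome defect, worth correcting because the correction is so cheap.

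**What to change.** - In Section 8.3, exempt the 15N-labelled species from the pre/post matched test, and make the matching change in 4.2 e and Aim 2 h. Leave 14NO2-cLA where it is.
- Report the labelled species at Visit 6 as estimates per matrix: concentration, or labelled share 15N/(14N+15N), with a 95% confidence interval, plus the proportion of participants above the detection limit. Use the Visit 3 samples as the assay blank.
- Keep the pre/post comparison for NO2-cLA, but specify it as total (14N+15N). The labelled dose replaces the regular one, so 14N alone at Visit 6 would leave out product of the last dose before sampling. Item 4.2 b already provides for NO2-cLA in BALF, plasma and urine.
- Reconcile the three statements of when the labelled dose is taken (Aim 2 h, the Section 5.2 footnote, and Visit 5), because the Visit 6 estimate depends on time since that dose.

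The cost is a few sentences and one fewer secondary p-value. No new samples or procedures are needed.
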